6.2.3 Justification for Dose Regimen

[REDACTED]

In the preceding study, 1 mg of TVP-1012 or placebo was administered for 26 weeks to evaluate the efficacy and safety of TVP-1012 1 mg.

In this study, the dose of 1 mg of TVP-1012 will be maintained for subjects treated with 1 mg of TVP-1012 in the preceding study, to evaluate administration at 1 mg for 52 weeks. In addition, subjects treated with placebo in the preceding study will be switched to 1 mg of TVP-1012 in this study, to evaluate administration at 1 mg for 26 weeks, for the purpose of evaluating a large number of subjects as much as possible.

[REDACTED]

CONFIDENTIAL

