6.2.4 Justification for Treatment Period

Parkinson's disease is a progressive disease and long-term administration is anticipated when TVP-1012 is prescribed. Therefore, another 26-week extension of treatment was planned following the 26-week treatment in the preceding study to evaluate the long-term safety of TVP-1012 for 6 months and 12 months.

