13.1.1 Analysis Sets

In this study, two kinds of analysis sets are defined: full analysis set (FAS) and safety analysis set. The safety analysis set, the analysis set used for safety analysis, will be defined as “all subjects who were received at least one dose of TVP-1012.” The definition of each analysis set will be described in the Handling Rules for Analysis Data.

The sponsor will verify the validity of the definitions of the analysis sets as well as the rules for handling data, consulting a medical expert as needed. If necessary, the Handling Rules for Analysis Data will be supplemented with new handling rules that were not discussed at the planning stage. The Handling Rules for Analysis Data must be finalized prior to database lock.

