13.3 Determination of Sample Size

Number of subjects to be enrolled in this study: approximately 182

[Justification of Sample size]

In the preceding study, the planned number of subjects to be randomized was a total of 240 (120 per group) and the planned number of subjects evaluable for the primary endpoint (change in the MDS-UPDRS Part II + Part III total score from baseline to Week 26 of the treatment period (LOCF)) was a total of 220 (110 per group).

Since this study is a long-term extension study in patients with early Parkinson's disease who have completed the 26-week treatment period in the preceding study, considering the potential dropouts in the preceding study, approximately 182 subjects will be enrolled in this study.

In addition, considering the potential dropouts in this study and in the preceding study, it is estimated that 155 subjects will be treated with 1 mg of TVP-1012 for 26 weeks and 59 subjects for 52 weeks.

CONFIDENTIAL

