## **Considerations**

This is a multicenter, open-label, long-term, extension, phase 3 study that evaluates the safety and efficacy of long-term administration of TVP-1012 at 1 mg for another 26 weeks in patients with early Parkinson's disease who have completed the 26-week treatment period in the preceding TVP-1012/CCT-001 study.

The analyses for this study will be performed using pooled data from the preceding study and this study based on data obtained after administration of TVP-1012, unless otherwise specified.

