#### 3.1 Treatment-Emergent Adverse Event

##### 3.1.1 Overview of Treatment-Emergent Adverse Events

Analysis Set: Safety Analysis Set

Analysis Variable(s): TEAEs that occurred after administration of TVP-1012

Categories: Relationship to Study Drug [Related, Not Related]  
Intensity [Mild, Moderate, Severe]

Analysis Method(s): The following summaries will be provided for each treatment group in the preceding study.

- (1) Overview of TEAEs
  - 1) All TEAEs (number of events, number and percentage of subjects)
  - 2) Relationship of TEAEs to study drug (number of events, number and percentage of subjects)
  - 3) Intensity of TEAEs (number of events, number and percentage of subjects)
  - 4) TEAEs leading to study drug discontinuation (number of events, number and percentage of subjects)
  - 5) Serious TEAEs (number of events, number and percentage of subjects)
  - 6) Relationship of serious TEAEs to study drug (number of events, number and percentage of subjects)
  - 7) Serious TEAEs leading to study drug discontinuation (number of events, number and percentage of subjects)
  - 8) TEAEs resulting in death (number of events, number and percentage of subjects)

TEAEs will be counted according to the rules below.

[Number of subjects with TEAEs]

- In case of “frequency distributions by relationship to study drug”  
A subject with occurrences of a TEAE in both categories (i.e., Related and Not Related) will be counted once in the Related category.
- In case of “frequency distributions by intensity”  
A subject with multiple occurrences of a TEAE will be counted once for the TEAE with the maximum intensity.
- In case of distributions other than the above  
A subject with multiple occurrences of a TEAE will be counted only once.

[Number of events]

For each summary, the total number of events will be calculated.

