Analysis Method(s):	
The following summaries will be provided for each treatment group in the preceding study.
 
TEAEs will be coded using MedDRA and will be summarized using SOC and PT. SOC will be sorted alphabetically and PT will be sorted in decreasing frequency for tables provided by SOC and PT. SOC and PT will be sorted in decreasing frequency for tables provided by SOC only or PT only.
 
 
(1) All TEAEs by SOC and PT
 
(2) All TEAEs by SOC
 
(3) All TEAEs by PT
 
(4) Drug-Related TEAEs by SOC and PT
 
(5) Intensity of All TEAEs by SOC and PT
 
(6) Intensity of Drug-Related TEAEs by SOC and PT
 
(7) TEAEs Leading to Study Drug Discontinuation by SOC and PT
 
(8) Serious TEAEs by SOC and PT
 
(9) TEAEs by SOC and PT Over Time
 
 
The methods of counting events and calculating the percentage of subjects when conducting each frequency distribution will be as follows:
 
[Number of subjects with TEAEs]
 
 
• In case of “frequency distributions by SOC and PT, by SOC only, or PT only”
 
 
A subject with multiple occurrences of TEAE within a SOC will be counted only once in that SOC.
 
A subject with multiple occurrences of TEAE within a PT will be counted only once in that PT.
 
When calculating percentages for TEAE, the number of subjects in the safety analysis set will be used as the denominator.
 
 
• In case of “frequency distributions by SOC and PT”
 
 
A subject with multiple occurrences of a TEAE within a SOC or a PT will be counted only once for the TEAE with the maximum intensity.
 
When calculating percentages for TEAE, the number of subjects in the safety analysis set will be used as the denominator.
 
 
• In case of “frequency distributions by time of onset by SOC and PT”
 
 
For each time interval, a subject with multiple occurrences of TEAE within a SOC or a PT will be counted only once in that SOC or PT. When calculating the onset rate of TEAEs for each time interval, the number of subjects among the safety analysis set (i.e., subjects who either have an exposure or have an occurrence of a TEAE, during or after the corresponding time interval) will be used as the denominator and the number of subjects whose onset of any one of the TEAEs is within the time interval will be used as the numerator.

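### The main TEAE tables are crude percentages over unequal follow-up, so they estimate neither a 6-month nor a 12-month risk; rates and cumulative incidence should be added

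*SAP*

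**What the plan says.** The primary endpoint is the frequency of adverse events. Protocol 6.2.4 justifies the extension as a way to "evaluate the long-term safety of TVP-1012 for 6 months and 12 months".

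Protocol 13.1.1 defines the safety analysis set as "all subjects who were received at least one dose of TVP-1012". The SAP (Considerations) adds: "The analyses for this study will be performed using pooled data from the preceding study and this study". The 1 mg -> 1 mg column thus includes subjects who took 1 mg in the preceding study and never entered the extension.

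For the SOC and PT displays, SAP 3.1.2 says "The following summaries will be provided for each treatment group in the preceding study", and "When calculating percentages for TEAE, the number of subjects in the safety analysis set will be used as the denominator". The overview in SAP 3.1.1 asks for numbers and percentages of subjects but names no denominator.

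Display (9), TEAEs over time, is different. Within each interval it divides by subjects who have exposure or a TEAE in that interval or later. The protocol lists it among the primary-endpoint analyses (13.1.4).

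On exposure, Protocol 6.2.3 keeps former 1 mg subjects on the drug "to evaluate administration at 1 mg for 52 weeks", while former placebo subjects have 26 weeks. Protocol 13.3 expects that "155 subjects will be treated with 1 mg of TVP-1012 for 26 weeks and 59 subjects for 52 weeks". Routine AE collection ends at Week 52 or early termination (10.2.1.1).

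**The concern.** A subject who leaves early without an event stays in the denominator as if event-free for the whole period. In the 1 mg -> 1 mg column, about half of the 120 planned subjects are expected to leave before 52 weeks. The P -> 1 mg column has at most half the planned time on drug. A crude percentage then mixes risk with length of follow-up, differently in each column.

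This matters most for events that arise late, which an extension is meant to find. The stated interest is safety at 6 and 12 months, yet no TEAE output gives a cumulative risk at either time or a rate per unit of exposure.

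**Working it through.** **Inputs from the documents.** Protocol 13.3: 240 randomized (120 per group), 182 entering the extension, 155 treated for 26 weeks, 59 for 52 weeks. Dropout by arm and period is not stated.

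**The plan's own figures.** A single retention rate of 182/240 = 75.8% per 26 weeks gives 120 x 0.758 = 91 and then 91 x 0.758 = 69 at 52 weeks, and 91 + 69 = 160 for 26 weeks. These are not 59 and 155. Rates that differ by arm or period do fit, so the planned figures are feasible. Three fitting patterns serve as assumptions:

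- A: 1 mg 120 -> 91 -> 59; placebo entrants 91 -> 64 (91 + 64 = 155).
- B: 1 mg 120 -> 84 -> 59; placebo entrants 98 -> 71 (84 + 71 = 155).
- C: 155 read as extension completers: 1 mg 120 -> 69 -> 59; placebo entrants 113 -> 96 (59 + 96 = 155).

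**Formula.** Assume the same constant hazard in both columns, lambda = -ln(1 - R)/52 per week for a true 52-week risk R. Assume independent exponential dropout at rate mu in each segment of length L = 26 weeks, with S the share still followed and event-free at the start of the segment. The crude percentage is the sum over segments of S x lambda/(lambda + mu) x (1 - exp(-(lambda + mu)L)).

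**One case in full (A, R = 20%).** lambda = 0.00429; mu = 0.01064 in the first segment and 0.01667 in the second. The first segment contributes 9.25%. S is then 0.678, and the second segment contributes 5.83%. The total is 15.1% against a true 20%. For P -> 1 mg, mu = 0.01354 and the result is 8.9% against a true 26-week risk of 10.6%.

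**Results** (1 mg -> 1 mg / P -> 1 mg):

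| Pattern | Mean weeks on drug | True 52-week risk 10% | 20% | 50% | Column ratio, R from 2% to 80% |
|---|---|---|---|---|---|
| A | 38.7 / 21.9 | 7.5% / 4.3% | 15.1% / 8.9% | 38.7% / 24.9% | 1.76 to 1.36 |
| B | 37.2 / 22.2 | 7.2% / 4.4% | 14.5% / 9.1% | 37.2% / 25.3% | 1.67 to 1.30 |
| C | 33.8 / 24.0 | 6.5% / 4.7% | 13.2% / 9.8% | 33.9% / 27.2% | 1.40 to 1.11 |

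Over R = 2% to 80%, the 1 mg -> 1 mg column shows 75-81% of the true risk in A, 72-78% in B and 65-72% in C. Placing all dropout at the start or the end of each segment moves a true 20% to between 10.7% and 17.7%, always below 20%.

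**Event timing (pattern A).** A 10% risk confined to Weeks 26-52 shows as 6.2%. A 20% risk confined to the first 84 days shows as 18.8% and 18.5% (ratio about 1.02). Confined to the first 28 days, it shows as 19.6% and 19.5%.

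**Display (9) (pattern A, R = 30%).** The first two 84-day intervals agree closely (7.4% and 7.3% in each). In Days 168-<252 the columns show 7.3% and 1.3%, because P -> 1 mg subjects have only about 14 of those 84 days on drug yet count in full.

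**With rates.** At R = 20%, both columns have an incidence of -ln(0.8) x 100 = 22.3 per 100 patient-years.

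**The case against.** The strongest reply is that the plan promises a frequency and delivers one. Section 6.2.4 justifies the treatment duration; it does not define a cumulative-risk estimand. The SAP specifies a group difference for efficacy (2.1.1.2) and none for TEAEs. Columns are labelled by regimen, and exposure is tabulated by group (SAP 1.3.1), so a reader can see that follow-up is unequal. Display (9) already handles late events. In the late-only case, a full interval such as Days 252-<336 would show about 4.3% against a true 4.7%.

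Much of this stands. No test or decision is affected, and the harm is misreading. Display (9) is a real partial remedy. But it gives no cumulative figure, omits serious, drug-related and discontinuation TEAEs, and dilutes P -> 1 mg in Days 168-<252. The exposure table is not linked to events, so first-event person-time cannot be recovered from it.

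A reader might infer that every primary TEAE percentage ignores follow-up, or that 1 mg -> 1 mg is bound to look much worse. Display (9) contradicts the first. The second depends on event timing and on a split by arm that the protocol does not give. Nor can the ever-dosed denominator be read into SAP 3.1.1, which is silent.

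**Conclusion.** The point holds for displays (1)-(8), and for SAP 3.1.1 if it uses the same denominator. These percentages are descriptive counts over mixed follow-up and should not be read as 6-month or 12-month risks. For events that keep arising, the direction of the understatement was the same in every dropout pattern and timing tried. Its size rests on assumed dropout splits, constant hazard and independent dropout.

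The understatement refers to risk under continued treatment, with leavers keeping a similar hazard. It is smaller where the adverse event itself caused the exit, because that event is already counted. The 155 and 59 are not shown to be wrong. This is a cheap improvement to reporting, not a flaw in a planned inference.

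**What to change.** Keep the crude tables and make these changes in the SAP:

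1. State the denominator in 3.1.1.
2. By group, add first-onset incidence per 100 patient-years of TVP-1012 follow-up with exact 95% CI, for the main 3.1.1 rows and for PTs reported in at least 3 subjects.
3. Add cumulative incidence from first TVP-1012 dose, with 95% CI and numbers at risk, for any, drug-related and serious TEAEs and for those PTs. Read it at about Day 174 in both groups and Day 356 in 1 mg -> 1 mg, just before the visit windows open (Days 175-189 and 357-371, Protocol Appendix A). At Day 182 or 364, completers seen early would already be censored. In P -> 1 mg, a Week 26 visit on Day 189 and a Week 52 visit on Day 357 leave only 357 - 189 = 168 days, so numbers at risk must be shown there.
4. For TEAEs leading to discontinuation or death, use a competing-event (Aalen-Johansen) estimate, or give the crude percentage and rate only. Stopping for another reason rules out a later discontinuation TEAE and should not be treated as independent censoring.
5. Footnote the crude tables: the columns have unequal follow-up and are not to be compared directly.

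The cost is SAP wording and a few outputs from dates already collected. The rates assume a roughly constant hazard, and the cumulative estimates assume dropout unrelated to AE risk; both should be footnoted.

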
### 3.1.3 Examination of Subgroups for Treatment-Emergent Adverse Event

Analysis Set: Safety Analysis Set

Analysis Variable(s): TEAEs that occurred after administration of TVP-1012

Subgroup(s):

Age (years)	[Min<= - <65, 65<= - <=Max]
Gender	[Male, Female]
Smoking history	[Yes, No]
Timing of Study Drug	[Before breakfast, After breakfast]
Administration	

Analysis Method(s): The following summaries will be provided for above each subgroup by treatment group in the preceding study.  
 TEAEs will be coded using MedDRA and will be summarized using SOC and PT, where SOC will be sorted alphabetically and PT will be sorted in decreasing frequency.

- (1) All TEAEs by SOC and PT
- (2) Drug-Related TEAEs by SOC and PT

The methods of counting events and calculating the percentage of subjects when conducting each frequency distribution will be as follows:  
 [Number of subjects with TEAEs]

- A subject with multiple occurrences of TEAE within a SOC will be counted only once in that SOC.
- A subject with multiple occurrences of TEAE within a PT will be counted only once in that PT.

When calculating percentages for TEAE, the number of subjects in each stratified item in the safety analysis set will be used as the denominator.

## 3.2 Laboratory and Other Safety Data

### 3.2.1 Laboratory Test Results

#### 3.2.1.1 Hematology and Serum Chemistry

Analysis Set: Safety Analysis Set

Analysis Variable(s): Hematology

RBC	Hemoglobin	Hematocrit
WBC		
WBC Differentials (Neutrophil, Eosinophil, Monocyte, Lymphocyte, and Basophil)		
Platelets		
Serum Chemistry		
AST	ALT	γ-GTP
ALP	LDH	Albumin
Total Protein	Total Bilirubin	Total Cholesterol
Triglycerides	Creatinine	
Blood Urea Nitrogen (BUN)		Urine Acid
Creatine Kinase		Sodium
Potassium	Chlorine	Calcium
Phosphorus		

Categories: Results of determination based on reference values  
 [Below lower limit of reference value, Within the range of reference value, Over upper limit of reference value]

Visit:	Baseline (prior to TVP-1012 administration), Week 3, Week 6, Week 14, Week 20, Week 26, Week 29, Week 32, Week 40, Week 46, Week 52
Analysis Method(s):	The following summaries will be provided for each treatment group in the preceding study.
	
 
(1) Descriptive statistics for observed values for each visit and changes (each visit after administration [Week 3 to Week 52] - baseline [prior to TVP-1012 administration]) will be provided.
 
(2) Case Plots
 
(3) A shift table for baseline (prior to TVP-1012 administration) and each visit after administration will be provided for the results of determination based on the reference values.
 

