7.5 Criteria for Discontinuation or Withdrawal of a Subject

The primary reason for discontinuation or withdrawal of the subject from the study should be recorded in the case report form ([e]CRF) using the following categories. For screen failure subjects, refer to Section 9.1.15.

1. Pretreatment Event or AE

The subject has experienced a pretreatment event (PTE) or AE that requires early termination because continued participation imposes an unacceptable risk to the subject's health or the subject is unwilling to continue because of the PTE or AE.

- Liver Function Test (LFT) Abnormalities
- Study medication should be discontinued immediately with appropriate clinical follow-up until a subject's laboratory profile has returned to normal or the value immediately after the informed consent (for PTEs), or the value before the initiation of the investigational drug* (for AEs). (See Section 9.1.9) if the following circumstances occur at any time during study medication treatment:

* The value before the initiation of the study medication is defined as the value prior to the start of the run-in period in the preceding study for AEs occurred before first study medication administration in the treatment period in the preceding study, and as the value at baseline in the preceding study for AEs occurred after first study medication administration in the treatment period in the preceding study.

- ALT or AST $> 8 \times$ ULN, or
- ALT or AST $> 5 \times$ ULN and persists for more than 2 weeks, or
- ALT or AST $> 3 \times$ ULN in conjunction with elevated total bilirubin $> 2 \times$ ULN or international normalized ratio (INR) > 1.5 , or
- ALT or AST $> 3 \times$ ULN with appearance of fatigue, nausea, vomiting, right upper quadrant pain or tenderness, fever, rash and/or eosinophilia ($> 5\%$).

2. Significant protocol deviation

The discovery after the first dose of study medication that the subject failed to meet protocol entry criteria or did not adhere to protocol requirements, and continued participation poses an unacceptable risk to the subject's health.

3. Lost to follow-up

The subject did not return to the clinic and attempts to contact the subject were unsuccessful. Attempts to contact the subject must be documented.

4. Voluntary withdrawal

The subject wishes to withdraw from the study. The reason for withdrawal, if provided, should be recorded in the (e)CRF.

CONFIDENTIAL

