9.1.9 Procedures for Clinical Laboratory Samples

Table 9.a lists the samples to be collected for each laboratory test. All samples will be collected after fasted for more than 8 hours, whenever possible, in accordance with acceptable laboratory procedures. The maximum volume of blood at any single visit is approximately 6 mL.

Table 9.a Clinical Laboratory Tests

Hematology	Serum Chemistry	Urinalysis
Red blood cells	AST	Protein (qualitative)
Hemoglobin	ALT	Glucose (qualitative)
Hematocrit	γ -GTP	Blood (qualitative)
White blood cells with differential (neutrophil, eosinophil, monocyte, lymphocyte, and basophil)	ALP	Ketone body (qualitative)
Platelets	LDH	
	Albumin	
	Total protein	
	Total bilirubin	
	Total cholesterol	
	Triglycerides	
	Creatinine	
	Blood urea nitrogen (BUN)	
	Urine acid	
	Creatine kinase	
	Sodium	
	Potassium	
	Chlorine	
	Calcium	
	Phosphorus	
Pregnancy Test (for female subjects of childbearing potential only)		
Urine hCG (qualitative)		

The central laboratory will perform laboratory tests for hematology, serum chemistries, and urinalysis. However, the urine hCG (qualitative) will be performed at each study site for women with childbearing potential.

If subjects experience ALT or AST $> 3 \times$ ULN, follow-up laboratory tests (at a minimum, serum ALP, ALT, AST, total bilirubin, γ -GTP, and INR) should be performed within a maximum of 7 days and preferably within 48-72 hours after the abnormality was noted. (see Section 7.5 and 10.2.3)

If the ALT or AST remains elevated $> 3 \times$ ULN on these 2 consecutive occasions, the investigator or sub-investigator must contact the sponsor for consideration of additional testing, close monitoring, possible discontinuation of study medication, discussion of the relevant subject details and possible alternative etiologies.

The laboratory test results will be evaluated and maintained by the investigator or sub-investigator. And also, the investigator will maintain a copy of the reference ranges for the laboratory used.

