10.1.3 Additional Points to Consider for PTEs and AEs

An untoward finding generally may:

- Indicate a new diagnosis or unexpected worsening of a pre-existing condition. (Intermittent events for pre-existing conditions underlying disease should not be considered PTEs or AEs.)
- Necessitate therapeutic intervention.
- Require an invasive diagnostic procedure.
- Require discontinuation or a change in dose of study medication or a concomitant medication.
- Be considered unfavorable by the investigator for any reason.

Diagnoses vs signs and symptoms:

Each event should be recorded to represent a single diagnosis. Accompanying signs (including abnormal laboratory values or ECG findings) or symptoms should NOT be recorded as additional AEs. If a diagnosis is unknown, sign(s) or symptom(s) should be recorded appropriately as a PTE(s) or as an AE(s).

Laboratory values and ECG findings:

Changes in laboratory values or ECG parameters are only considered to be PTEs or AEs if they are judged to be clinically significant (i.e., if some action or intervention is required or if the investigator or sub-investigator judges the change to be beyond the range of normal physiologic fluctuation). A laboratory re-test and/or continued monitoring of an abnormal value are not considered an intervention. In addition, repeated or additional noninvasive testing for verification, evaluation or monitoring of an abnormality is not considered an intervention.

If abnormal laboratory values or ECG findings are the result of pathology for which there is an overall diagnosis (e.g., increased creatinine in renal failure), the diagnosis only should be reported appropriately as a PTE or as an AE.

Pre-existing conditions (disease or symptom present before signing of the informed consent in the preceding study):

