10.2.3 Reporting of Abnormal Liver Function Tests

If a subject is noted to have ALT or AST $> 3 \times$ ULN and total bilirubin $> 2 \times$ ULN for which an alternative etiology has not been identified, the event should be recorded as a SAE and reported as per Section 10.2.2. The investigator or sub-investigator must contact the Medical Monitor for discussion of the relevant subject details and possible alternative etiologies, such as acute viral hepatitis A or B, other acute liver disease, or a history or concurrent medical condition. Follow-up laboratory tests as described in Section 9.1.9 must also be performed.

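### The SAP plans no per-subject count of ALT/AST above 3x, 5x or 8x ULN, or of ALT/AST above 3x with bilirubin above 2x ULN, although the protocol acts on these levels

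*SAP*

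**What the plan says.** **Protocol actions.** Under section 9.1.9, ALT or AST above 3x ULN triggers follow-up tests that "should be performed within a maximum of 7 days and preferably within 48-72 hours after the abnormality was noted". If the value is still above 3x "on these 2 consecutive occasions, the investigator or sub-investigator must contact the sponsor for consideration of additional testing". Under section 7.5, drug is stopped in four situations:

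- ALT or AST above 8x ULN;
- above 5x ULN "and persists for more than 2 weeks";
- above 3x ULN "in conjunction with elevated total bilirubin" (above 2x ULN), or with INR above 1.5;
- above 3x ULN with listed symptoms or eosinophilia.

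Under section 10.2.3, ALT or AST above 3x with bilirubin above 2x ULN "for which an alternative etiology has not been identified, the event should be recorded as a SAE".

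**Adverse-event rule.** Section 10.1.3 makes a laboratory change an AE only when it is clinically significant: some action is needed, or "if the investigator or sub-investigator judges the change to be beyond the range of normal physiologic fluctuation". A repeat test does not count as an intervention.

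**SAP outputs.** For each analyte, section 3.2.1.1 gives by-visit descriptive statistics, case plots and a shift table with the categories "Below lower limit of reference value, Within the range of reference value, Over upper limit of reference value". The visit-window rules keep one value per window, the one nearest the scheduled day, with ties going to the later value. The only per-subject count of ever crossing a limit is the markedly-abnormal-value summary in section 3.2.2.1. Appendix 2 defines its criteria for temperature, blood pressure and pulse only.

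**The concern.** Long-term safety is the primary objective and laboratory values are a secondary endpoint. A natural question for the study report is how many subjects on TVP-1012 ever exceeded each liver threshold, and how many had the joint rise. The protocol treats these levels as important enough to act on, yet no planned table answers the question directly. By-visit tables cannot be added up into subjects, because one person may be high at several visits. Separate tables for ALT, AST and bilirubin do not show whether high values belong to the same person.

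**Working it through.** There is no stated figure to reproduce: the study is descriptive and the documents give no laboratory event rate. The check sets the outputs side by side, then sizes the missing table.

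**1. What the shift table can separate.** Values of 1.1x, 3.1x, 5.1x and 8.1x ULN all fall in the over-limit category. The count in that category is therefore a ceiling on the number above 3x for that analyte and visit, but not the number itself.

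**2. Where each kind of case would surface.**

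| Case | Planned output that should show it |
|---|---|
| Meets a section 7.5 stopping rule before the last visit | Discontinuation reason (SAP 1.1.5, 1.1.6.2); TEAEs leading to discontinuation (SAP 3.1.2), if recorded as an AE |
| Joint rise without another etiology | Serious TEAEs (SAP 3.1.2) |
| Isolated rise above 3x, not judged clinically significant | No count |
| Rise above 5x lasting 2 weeks or less, not judged clinically significant | No count |
| Peak not selected within its window | Absent from the by-visit statistics and shift table |

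The first two rows count reasons or coded terms, not threshold crossings.

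**3. How a peak can be dropped.** Take Week 40: scheduled Day 280, laboratory window Days 252 to 300. Suppose a sample is drawn on Day 274, noted as abnormal on Day 276 and retested on Day 279. The distances from schedule are |274 - 280| = 6 and |279 - 280| = 1. The retest is tabulated, and the Day 274 value is not, even if it was the peak. Conversely, with a first sample on Day 280 and a retest on Day 287, the distances are 0 and 7, so a higher retest value would be dropped.

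More generally, let the retest come k days after the visit. For the 1 mg to 1 mg group at Weeks 29, 32, 40, 46 and 52, I counted the permitted visit days d (15 days, s - 7 to s + 7, where s is the scheduled day) on which the retest lies in the same window and |d + k - s| <= |d - s|. The retest replaces the first value on 7 of 15 days at k = 2, 6 at k = 3, 4 at k = 7, 1 at k = 14 and none at k = 15. The value of k is laboratory turnaround, which is not stated (assumed 0 to 7 days), plus a retest lag of 2 to 7 days. These are counts of days, not probabilities, and they apply only if the retest is evaluable.

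**4. Denominator of a per-subject table.** The safety set is everyone with at least one dose of TVP-1012, pooled over both studies. Protocol section 13.3 plans 120 randomized to 1 mg and about 182 entering the extension. If the 182 split equally, 91 switch from placebo. Then 120 + 91 = 211, provided all are dosed and measured.

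**5. Precision at n = 211 (exact one-sided 95% upper limit).**

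- No case: 1 - 0.05^(1/211) = 1.41%.
- One case: the p that solves (1 - p)^211 + 211 p (1 - p)^210 = 0.05, which is 2.23%.

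The protocol's expected exposure counts, 155 for 26 weeks and 59 for 52 weeks, describe treatment duration. They are not this table's denominator.

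**The case against.** The strongest reply is that the important cases are already caught. A joint rise requires stopping drug whatever its cause and, without another etiology, must be an SAE. Sustained rises above 5x and any rise above 8x also stop drug. That stands. A reader might infer from the missing table that serious liver injury would go unseen, and the documents do not support that. The cover is incomplete at the edges: a joint rise found at the final visit and explained by another etiology leads neither to early stopping nor to a mandatory SAE.

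The second reply is that the existing laboratory outputs bound the answer. This also stands. From maximum and quartiles alone, with 59 subjects and a Week 52 maximum above 3x ULN, one might infer anything from 1 to 14 crossings: 0.75 x 59 = 44.25, so the upper quartile is the 45th ordered value and 14 lie above it. But the shift table reports how many were over the limit at that visit, and case plots may show the individual points. The remaining uncertainty is usually much smaller.

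Third, protocol section 13.1.4 asks only for descriptive statistics, plots and shift tables, and the SAP supplies all three. It would be wrong to call this a contradiction between the two documents. Nor does the visible text support a liver concern specific to this drug, since the background safety summary is redacted.

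Lastly, the loss of peaks is hypothetical. Turnaround, the evaluability of retests (left to the Handling Rules for Analysis Data) and the place where retests are stored are not stated. If retests are not in the database, a new table cannot recover them.

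**Conclusion.** The point holds as a modest reporting gap. No planned output counts subjects above 3x, 5x or 8x ULN or with the joint rise. The cases that escape every planned count are mainly isolated rises above 3x, or transient rises above 5x, that the investigator does not judge clinically significant; peaks that lose the window selection can also be missed. The number of such cases cannot be estimated from the documents.

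With about 211 subjects, a per-subject table would support an upper limit of 1.4% if nobody crossed a threshold and 2.2% if one did. This rests on the planned numbers, an equal split of the 182, and complete dosing and measurement.

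A reader might take such a table as the number meeting the protocol's stopping rules. It would not be: those rules also involve persistence beyond 2 weeks, INR, symptoms and eosinophilia.

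**What to change.** Add one table to SAP section 3.2.1.1, by preceding-study group and combined, and leave the existing tables unchanged.

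- **Data:** all evaluable values, scheduled and unscheduled, from the first TVP-1012 dose to 7 days after the last, each compared with the ULN of the laboratory that ran the sample.
- **Rows (n, %):** ALT or AST above 3x ULN; above 5x; above 8x; ALT or AST above 3x with total bilirubin above 2x ULN on the same sample date.
- **Denominator:** subjects with at least one evaluable value after TVP-1012; for the joint row, both tests on one date.
- **Label:** threshold crossings, with a note that persistence, INR, symptoms and eosinophilia are not applied.
- **Footnote:** any retests missing from the database.

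The per-subject rule in Appendix 2 is a ready model, but it works one test item at a time, so the joint row needs the same-date rule written out. Scheduled results come from the central laboratory. For retests run elsewhere, section 9.1.9 says "the investigator will maintain a copy of the reference ranges for the laboratory used". The cost is a short SAP addition and one table that will probably be sparse. There is no hypothesis test, so no error rate is affected.
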